### 5.2 Secondary Endpoints

- Serious angiographic complications (flow-limiting dissection, perforation, distal embolization, or acute vessel closure) as assessed by the angiographic core lab
- Lesion Success defined as final residual stenosis  $\leq 50\%$  in the target lesion without serious angiographic complications as assessed by the angiographic core lab
- Primary Patency at 6 and 12 months as assessed by both subject and lesion level defined as the absence of both total occlusion (100% diameter stenosis as assessed by DUS core lab) in all of the target lesions in a flow pathway, as well as any CEC adjudicated Clinically-Driven Target Lesion Revascularization (CD-TLR)
- Clinically-Driven Target Lesion Revascularization (CD-TLR), CEC adjudicated, at 30 days, 6, 12, & 24 months
- Major Adverse Events (MAE), CEC adjudicated, at 30 days defined as a composite of:
  - Need for emergency surgical revascularization of target limb
  - Unplanned target limb major amputation (above the ankle)
  - Symptomatic thrombus or distal emboli that require surgical, mechanical, or pharmacologic means to improve flow, and extend hospitalization

	No.: CP 65007	REV. C
	TITLE: Disrupt PAD BTK II Study	
	CLASS: CLINICAL PROTOCOL	PAGE 20 OF 71

- Perforations that require an intervention, including bail-out stenting
- Quality of Life (QoL) assessed by VascuQoL questionnaire at 30 days, 6, 12, & 24 months, reported as change from baseline
- Major Target Limb Amputation, CEC adjudicated, at 30 days, 6, 12, & 24 months
- Ankle-brachial index (ABI) or toe-brachial index (TBI) at 30 days, 6, 12, & 24 months, reported as change from baseline
- Rutherford Category at 30 days, 6, 12, & 24 months, reported as change from baseline
- Number of existing, new, and recurrent wounds at 30 days, 6, 12, & 24 months
- Number of healed wounds at 30 days, 6, 12, & 24 months
- Number of non-healed wounds by category (improving, stagnant, worsening) at 30 days, 6, 12, & 24 months

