#### General Exclusion Criteria

1. Rutherford Clinical Category 0, 1, 2, and 6 (target limb).
2. Subjects with osteomyelitis or deep soft tissue infection are excluded unless infection can be treated with an individual toe ray amputation or transmetatarsal amputation (TMA) in the target limb in the opinion of the investigator.
3. History of endovascular or surgical procedure on the target limb within the last 30 days, or planned within 30 days of the index procedure with the exception of toe amputation(s).
4. Subject in whom antiplatelet or anticoagulant therapy is contraindicated.
5. Subject has known allergy to contrast agents or medications used to perform endovascular intervention that cannot be adequately pre-treated.
6. Subject has known allergy to urethane, nylon, or silicone.
7. Myocardial infarction within 30 days prior to enrollment.
8. History of stroke within 60 days prior to enrollment.

	No.: CP 65007	REV. C
	TITLE: Disrupt PAD BTK II Study	
	CLASS: CLINICAL PROTOCOL	PAGE 25 OF 71

9. Subject has acute or chronic renal disease with eGFR <30 ml/min/1.73m^2 (using CKD-EPI formula), unless on renal replacement therapy.
10. Subject is pregnant or nursing.
11. Subject is participating in another research study involving an investigational agent (pharmaceutical, biologic, or medical device) that has not reached the primary endpoint.
12. Subject has other medical, social or psychological problems that, in the opinion of the investigator, preclude them from receiving this treatment, and the procedures and evaluations pre- and post-treatment.
13. Covid-19 diagnosis within 30 days.
14. The planned use of cutting/scoring balloons, re-entry or atherectomy devices in target lesions during the index procedure.
15. Planned major amputation (of either leg).
16. Acute limb ischemia (of either leg).
17. Occlusion of all the inframalleolar outflow arteries/vessels (i.e., desert foot) in the target limb.
18. Subject has an anticipated life span of less than one (1) year.
19. Subject already enrolled into this study.

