## 7.6 Screening/Baseline Procedures

Baseline assessments must be completed within 30 days of the procedure. The following are exceptions: wound assessment which can be completed within 45 days of procedure, ankle-brachial index (ABI) / toe-brachial index (TBI), which can be completed within 60 days of the procedure, and a pregnancy test which must be done within 7 days of the procedure. Informed consent must be obtained prior to any study-specific evaluations needed to assess eligibility which are not considered standard of care. Subjects on warfarin or direct thrombin inhibitors should be followed per institutional standard of care by the physician.

Baseline assessments include:

- Medical history
- Physical examination

	No.: CP 65007	REV. C
	TITLE: Disrupt PAD BTK II Study	
	CLASS: CLINICAL PROTOCOL	PAGE 30 OF 71

- Vital signs
- Height and weight
- Baseline Labs (eGFR)
- ABI or TBI (at rest; use same test for subject throughout study)
- Rutherford Category
- VascuQoL-6 Questionnaire
- Wound Healing Assessment (including photographs)
- Review of medications (anticoagulants and antiplatelets)
- Urine pregnancy test if female of child-bearing age

*Note: If treatment of two target lesions is planned across both limbs, the RC category and ABI/TBI for each limb must be assessed. If ABI/TBI cannot be assessed due to non-compressible vessels, this should be documented. If TBI is used, subject should have TBI at each follow-up visit.*

eGFR should be calculated using the CKD-EPI formula in absence of a standardized lab test provided by the site.

Wound healing assessments of the target limb(s) must be performed at baseline and all follow-up visits. Photographs must be taken of the wound(s) to document the progression of wound healing throughout the study and kept in the subject's study binder. Photographs will be retained at the site in the study subject's medical record but will not be provided to the Study Sponsor via upload. If photographs are not obtained, a protocol deviation will be issued. At the follow-up visits, the wounds will be recorded in the EDC as healed (completely epithelialized), not healed, recurrent, new, or amputated. If the wound is not healed, it will be further classified as improving, stagnant, or worsening. A wound can only be considered recurrent if it was healed at a prior study visit and subsequently re-appears at the same location.

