### 15.1 Study Definitions

**Abrupt or Acute Closure:** Angiographic documentation of significantly reduced flow due to mechanical dissection, thrombus, or severe vessel spasm in the treatment area.

**Acute Limb Ischemia:** A sudden decrease in limb perfusion that causes a potential threat to limb viability (manifested by ischemic rest pain, ischemic ulcers, and/or gangrene) in patients who present within two weeks of the acute event.

**Adverse Device Effect (ADE):** Adverse event related to the use of an investigational medical device.

*Note: This definition includes adverse events resulting from insufficient or inadequate instructions for use, deployment, implantation, installation, or operation, or any malfunction of the investigational medical device.*

*Note: This definition includes any event resulting from use error or from intentional misuse of the investigational medical device.*

*Note: This includes “comparator” if the comparator is a medical device.*

**Adverse Event (AE):** Untoward medical occurrence, unintended disease or injury, or untoward clinical signs (including abnormal laboratory findings) in subjects, users or other persons, whether or not related to the investigational medical device and whether anticipated or unanticipated.

*Note: This definition includes events related to the investigational medical device or the comparator.*

*Note: This definition includes events related to the procedures involved.*

*Note: For users or other persons, this definition is restricted to events related to the use of investigational medical devices or comparators.*

**Amputation (major):** Any requirement for amputation above the ankle.

**Amputation (minor):** Any requirement for amputation below the ankle.

**Amputation, Unplanned:** An amputation associated with the target limb that occurs between the index procedure and 30 days post-procedure that was not previously planned as part of the overall treatment strategy.

**Ankle-Brachial Index (ABI):** The ratio of systolic blood pressure measured at the ankle to systolic blood pressure measured at the brachial artery.

**Below the Knee (Lesion Location):** From center of knee joint space to ankle joint.

**Calcification Classification (PARC):** Calcification will be assessed by the angiographic core lab according to the Peripheral Academic Research Consortium (PARC) definition [21].

	No.: CP 65007	REV. C
	TITLE: Disrupt PAD BTK II Study	
	CLASS: CLINICAL PROTOCOL	

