Note: Device crossing failures or device malfunction causing no actual IVL treatment are still considered target lesions.

	No.: CP 65007	REV. C
	TITLE: Disrupt PAD BTK II Study	
	CLASS: CLINICAL PROTOCOL	PAGE 63 OF 71

**Target Lesion Revascularization, Clinically-driven (TLR):** A target lesion revascularization performed due to target lesion diameter stenosis  $\geq 50\%$  and either evidence of clinical or functional ischemia (e.g., recurrent/progressive life-limiting intermittent claudication, claudication unresponsive to medical therapy, CLI) or recurrence of the clinical syndrome for which the initial procedure was performed. Clinically driven target lesion revascularization occurs in the absence of protocol directed surveillance ultrasound or angiography.

**Target Vessel Revascularization, Clinically-driven (TVR), non-TLR:** A target vessel revascularization performed due to non-target lesion diameter stenosis  $\geq 50\%$  and either evidence of clinical or functional ischemia (e.g., recurrent/progressive life-limiting intermittent claudication, claudication unresponsive to medical therapy, CLI) or recurrence of the clinical syndrome for which the initial procedure was performed. Clinically driven target vessel revascularization occurs in the absence of protocol directed surveillance ultrasound or angiography.

**Total Occlusion:** A 100% stenotic lesion as documented by angiographic absence of flow.

**Toe Brachial Index (TBI):** The ratio of systolic blood pressure measured at the toe to systolic blood pressure measured at the brachial artery.

**Unanticipated Serious Adverse Device Effect (USADE):** Serious adverse device effect which by its nature, incidence, severity or outcome has not been identified in the current risk assessment.

*Note: Anticipated serious adverse device effect (ASADE) is an effect which by its nature, incidence, severity or outcome has been identified in the risk assessment.*

**Wound:** Foot ulcer or gangrene. After debridement and/or minor amputation, a wound is characterized as a healed wound when it is completely epithelialized.

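### A wound that epithelializes after minor amputation fits both the amputated code (7.6) and the healed definition (15.1), and amputated wounds enter none of the wound endpoints (5.2)

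*Combined protocol and SAP*

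**What the plan says.** Section 7.6 sets five follow-up codes: "the wounds will be recorded in the EDC as healed (completely epithelialized), not healed, recurrent, new, or amputated". It adds one sub-classification: "If the wound is not healed, it will be further classified as improving, stagnant, or worsening". There is no rule for a wound that fits two codes.

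The entry for Wound in section 15.1 states: "After debridement and/or minor amputation, a wound is characterized as a healed wound when it is completely epithelialized". Minor amputation is defined in the same section as "Any requirement for amputation below the ankle".

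Section 5.2, repeated in the study summary, lists three wound endpoints for the four visits from 30 days onward. The first counts wounds that are existing, new or recurrent. The second counts those that have healed. The third is given as: "Number of non-healed wounds by category (improving, stagnant, worsening) at 30 days, 6, 12, & 24 months".

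All three are counts. No healing percentage or denominator is defined. The amputation components and endpoints in sections 5.1.1 and 5.2 concern amputation above the ankle only.

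Minor amputation is foreseen. Exclusion 2 bars certain infections "unless infection can be treated with an individual toe ray amputation or transmetatarsal amputation (TMA) in the target limb", and exclusion 3 exempts toe amputation from the ban on procedures planned within 30 days. Wound photographs stay at the site and are not uploaded to the sponsor (7.6).

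**The concern.** Take a subject with a toe ulcer at baseline whose toe is amputated during follow-up, with a fully epithelialized site at 6 months. A site that reads 7.6 records *amputated*. A site that reads 15.1 records *healed*. Both have followed the protocol. In the first case the wound appears in none of the three wound endpoints. In the second it adds to the healed count and cannot be told apart from an ulcer that closed with the toe intact.

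The code is chosen at data entry, the photographs are held locally, and the protocol describes no core lab reading of wounds. Inconsistent coding would therefore be hard to correct centrally. What is at stake is whether the wound results, which matter most for subjects enrolled with tissue loss (Rutherford 5), can be read unambiguously. At least 80% of enrollment is Rutherford 4 or 5, because category 3 is capped at 20% (6.7). The share in category 5 is not given.

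A related gap is that healed counts are not linked to baseline wounds. A wound that first appears after the procedure and later heals adds to the number healed.

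**Working it through.** The documents state no wound figure, so there is nothing to reproduce. The check maps each possible outcome to the code, the definition and the endpoint.

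| Outcome at a visit | 7.6 code | 15.1 | 5.2 wound endpoint |
|---|---|---|---|
| Epithelialized, no amputation | healed | healed | healed count |
| Open, no amputation | not healed, with sub-category | not healed | non-healed count |
| Minor amputation, site fully epithelialized | amputated or healed | healed | none, or healed count |
| Minor amputation, site not epithelialized | amputated, or arguably not healed | not yet healed | none, or non-healed count |
| Major amputation | amputated | not covered | none |

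The first endpoint also counts existing wounds. That term is not one of the five codes and is not defined; read plainly, a removed wound is not an existing one.

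The direct collision is in row three. Rows four and five show that the amputated code has no place in the endpoints.

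**Direction, on assumed numbers.** Take 100 baseline wounds. Let H be the number healed without amputation (40 to 60), A the number amputated (5 to 20), and e the share of amputated sites that are fully epithelialized (0, 0.5 or 1). All three are assumptions; none comes from the documents.

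- (a) Amputated counted as not healed: H/100.
- (b) Coded amputated and left out of the percentage: H/(100 − A).
- (c) Section 15.1 rule: (H + eA)/100.

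With H = 50 and A = 10:

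- (a) 50/100 = 50.0%; counts are 50 healed, 50 non-healed.
- (b) 50/90 = 55.6%; counts are 50 healed, 40 non-healed.
- (c) 50/100 = 50%, 55/100 = 55% or 60/100 = 60% for e = 0, 0.5 or 1. At e = 1 the counts are 60 healed, 40 non-healed.

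Over the assumed range:

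- (b) − (a) is smallest at H = 40, A = 5: 40/95 − 40/100 = 42.1% − 40.0% = 2.1 points. It is largest at H = 60, A = 20: 60/80 − 60/100 = 75.0% − 60.0% = 15.0 points.
- (c) − (a) = eA/100, from 0 points (e = 0) to 20 points (e = 1, A = 20).
- (c) − (b) at H = 50, A = 10 is 60.0 − 55.6 = +4.4 points for e = 1 and 50.0 − 55.6 = −5.6 points for e = 0. Which of the two documented readings is more favorable depends on e.

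Three things follow. Under the amputated code the healed count does not change; the non-healed count falls by A. A percentage rises under that code only if amputated wounds are left out of the denominator; with all 100 baseline wounds kept in, it is H/100, the same as (a). None of the codings compared gives a lower healing result than (a).

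**The case against.** A reader might infer three stronger things that the documents do not support.

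- *Every amputated wound has two conflicting codes.* It does not. Section 15.1 applies only after minor amputation, and only once epithelialization is complete. It does not call an open stump healed and says nothing of major amputation. This is an unresolved overlap in one subset.
- *Losing tissue automatically raises the healing result.* It does not. The endpoints are counts, and under the 7.6 code the healed count stays the same. It rises only under 15.1, and only for epithelialized sites.
- *The distortion has a known size.* It has none. Any number of points rests on assumed counts and on the comparison rule. Counting removed wounds as not healed is a reasonable reference, but the protocol does not prescribe it.

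The other side can fairly add that limb loss is not hidden. Major amputation is in the primary safety endpoint, in the 30-day MAE composite if unplanned, and is a CEC-adjudicated secondary endpoint through 24 months. Adverse events, which would include minor amputations, are collected through 24 months (10.4.1). Section 9.1 defers clarifications to the SAP, and the case report forms are a separate attachment (18.0); either might settle the coding, and neither can be checked here. The wound endpoints are secondary and descriptive.

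All of this narrows the point but does not remove it. Minor amputation still has no endpoint, the two protocol statements still collide at data entry, and an analysis rule written later would have to work with codes already entered inconsistently.

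**Conclusion.** The point holds in limited form. For a wound fully epithelialized after minor amputation, 7.6 and 15.1 give different codes with no precedence, and amputated wounds are in no wound endpoint. The same outcome can be recorded differently across sites. Removed wounds can drop out of the non-healed count or be counted as healed, so apparent healing can look better than if they were counted as not healed.

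The size cannot be derived from the documents. The 0 to 20 point range is illustrative only: it rests on the assumed values of H, A and e, and for reading (b) on a percentage that the protocol does not define. Only secondary descriptive endpoints are affected. The matter should be corrected, but it does not threaten the study's primary conclusions.

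**What to change.** 1. Reconcile 7.6 and 15.1 with one stated precedence rule.
2. In 5.2, report wounds removed by amputation, minor and major, as their own row at each visit. Every baseline wound is then accounted for as healed without amputation, not healed, or amputated (epithelialized or not).
3. Use all baseline wounds as the denominator for any healing percentage, and report new and recurrent wounds separately.
4. Show healing with epithelialized post-amputation wounds counted as healed (the 15.1 rule) and, as a sensitivity analysis, with amputated wounds counted as not healed.

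Scoring planned and unplanned amputations differently is not advised: 15.1 defines unplanned amputation only up to 30 days, so the split has no documented basis at 6, 12 or 24 months.

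The cost is definition wording and minor table work, since the amputated code is already specified for the EDC. Whether the epithelialization status of an amputated site is already captured should be checked against the case report form. The reported healing figure may be lower.

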## 7.7 Index Procedure

The IVL treatment algorithm is described in the steps below and illustrated in Figure 2. Each investigative site will be using one generator and one connector cable for enrollment in accordance with the IFU. Multiple IVL catheters can be used per subject enrollment.

### 7.7.1 Procedural Imaging Requirements

An angiographic cine will be obtained for each lesion treated including pre-procedure, post-IVL and end of procedure. (If any non-target lesions are treated, an additional cine will be obtained prior to IVL treatment of any target lesion(s) to ensure no serious angiographic complications have occurred and that the subject still meets criteria to be enrolled.) All angiographic images must be submitted to the core lab for analysis. If intravascular imaging (i.e., IVUS) is performed, images from the three timepoints (baseline, immediately post-IVL, and end of procedure) should be submitted to the IVUS core lab for analysis.

	No.: CP 65007	REV. C
	TITLE: Disrupt PAD BTK II Study	
	CLASS: CLINICAL PROTOCOL	PAGE 31 OF 71

For subjects enrolled in the IVUS Sub-study, angiographic and IVUS images are required at three (3) timepoints: baseline, immediately post-IVL, and end of procedure. The core lab will provide separate angio and IVUS protocols to participating study centers.

#### **7.7.2 Assessment of Calcification**

Up to two (2) target lesions may be treated per subject. Calcification of the target lesion(s) may be assessed by angiography or IVUS. To meet eligibility requirements, angiography requires fluoroscopic evidence of calcification on parallel sides of the vessel and extending > 50% the length of the lesion. If assessed by IVUS, there must be  $\geq 270$  degrees of calcium over the course of at least 10mm. Note: if calcification does not meet imaging criteria, a lesion may be eligible if found to be non-dilatable, suggestive of calcification.

#### **7.7.3 Treatment of Non-Target Lesions**

Non-target lesions must be treated successfully prior to treatment of the target lesion(s). After the maximum number (2) of target lesions has been reached, any additional lesions should be assigned as non-target lesions. Non-target lesions may be treated with any commercially available device; treating a non-target lesion with a device that is not approved or considered investigational will result in a protocol deviation.

*Note: In the case where non-target lesions and target lesion are present in both limbs, non-target lesions should be treated successfully first per limb.*

Clinically significant inflow lesions in the ipsilateral iliac, femoral, or popliteal arteries must be treated with  $\leq 30\%$  residual stenosis and no serious angiographic complications (e.g., embolism). Significant non-target infra-popliteal lesions must be treated with  $\leq 50\%$  residual stenosis with no serious angiographic complications (e.g., embolism). If there are serious angiographic complications following treatment of non-target lesions, the subject should not be enrolled.

#### **7.7.4 Tandem Lesion(s)**

Tandem lesions (lesions  $< 3$  cm apart) are allowed if the total treated area covers the entire diseased segment. Total treated area is defined as the area treated by any PTA device (pre-dilatation, IVL, post-dilatation, or DCB). Each tandem lesion/diseased segment is considered one target lesion. As tandem lesions are considered one single target lesion, angiographic eligibility must be met as a single lesion.

#### **7.7.5 Definition of Enrollment**

The definition of enrollment is when the subject signs informed consent, meets all general & angiographic eligibility criteria, and the IVL catheter has been inserted over a 0.014" guidewire (which had been previously passed across the target lesion).

	No.: CP 65007	REV. C
	TITLE: Disrupt PAD BTK II Study	
	CLASS: CLINICAL PROTOCOL	PAGE 32 OF 71

### 7.7.6 Pre-IVL Dilatation (if required)

If the operator is unable to pass the IVL balloon across the lesion, a standard PTA balloon up to 2.5mm should be used for pre-dilatation prior to treatment with the IVL Balloon (not applicable for enrollment of non-dilatable lesions).

